9.5.3 Safety

Unless otherwise specified, safety analyses include all data collected, including after discontinuation of randomized treatment.

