9.5.3.1 Main safety endpoint: estimated GFR using the MDRD formula

The key secondary and safety variable is renal function as assessed by eGFR (MDRD formula). This will be evaluated at Month 12 by comparing the mean eGFR values between groups.

The MDRD formula is defined as follows ([Levey et al 2003](#)):

$$\text{GFR } [\text{mL/min}/1.73\text{m}^2] = 186.3 * (\text{C}^{-1.154}) * (\text{A}^{-0.203}) * \text{G} * \text{R}$$

C is the serum concentration of creatinine [mg/dL]

A is age [years]

G=0.742 when gender is **female**, otherwise G=1

R=1.21 when race is **black**, otherwise R=1.

Local laboratory serum creatinine values will be used for all renal function data analysis. Serum creatinine results are in units of umol/L, so the following formula should be used to convert to the required unit of mg/dL:

$$\text{C}[\text{mg/dL}] = \text{serum concentration of creatinine } [\text{umol/L}] / 88.4.$$

Estimated GFR will be determined and summarized in each part of the study.

Handling of missing values/censoring/discontinuations

The analysis will be made on the FAS population. The following imputation method will be applied for patients with missing eGFR values:

- Patients that lose their graft will be assigned a value of zero for their missing GFR value.
- Patients that die or are lost to follow-up with a functioning graft will have an imputed value using the last-observation-carried-forward (LOCF) method.
- For patients that discontinue randomized treatment the eGFR will be considered missing after applying the windows defined in [Section 9.4.1](#).

Graft loss patients do not have a functioning graft; hence the lowest possible GFR value (zero) will be assigned to such patients. In contrast, patients that die with a functioning graft, die for different reasons (e.g., suicide, car accident, cancer). Similarly, patients who are lost to follow-up have renal function, but missing values for various reasons (e.g., moving from the area or not being able to make the site visit during the Month 6 or Month 12 visit window). Patients who have a functioning graft at the time of death or are Lost to Follow-up with a functioning graft will be analyzed via an imputation method that employs LOCF.

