6.1.4 Supportive analyses

Kaplan-Meier estimates

In this analysis, patients who have not experienced tBPAR, will be censored with the censoring time as defined by the last contact day at or before the cut-off point (e.g., 1st IA Month 3 visit, 2nd IA Month 6 visit). The patients will be considered as completed at the date of their corresponding analysis cut-off point. In addition to the Kaplan-Meier plot, a log-rank test shall be performed to obtain estimates with CI's for each treatment arm and the difference between treatment arms.

During data review, it was noticed that some patients were switched from the randomized treatment to another regimen. Therefore in future IA's, more focus shall be placed on the Kaplan-Meier analysis.

Supportive Bayesian analysis

In addition the Bayesian analysis will be repeated with a model using a Poisson distribution to account for the patients that may switch treatment or discontinue early from the study. The following parametrization will be used:

The number of tBPAR events in group i is assumed to follow a Poisson distribution, i.e.

$$y_i = \text{Poisson}(\mu_i),$$

where μ_i is the expected number of events in group i, with

$$\mu_i = \lambda_{i,T} * t_{i,T},$$

with $t_{i,T}$ being the total follow up time in group i (times censored at treatment switch or discontinuation) up to analysis time point T and λ_i being the event rate in group i up to the analysis time point T. For sensitivity analysis of the primary analysis the analysis time point T is week 12 (i.e. week 13 visit, month 3 after transplantation). The probability of an tBPAR event occurring up to the analysis time point can then derived as $\theta_i = 1 - \exp(-\lambda_i * T)$.

The pre-defined success criteria is considered to be a difference in the probability of tBPAR between the CFZ533 arm and the control group of less than 20 percentage points with at least 60% level of proof.

$$\Pr(\theta_{CFZ533} - \theta_{SoC} < 0.20 | \text{data}) > 60\%$$

The required posterior probabilities will be estimated from simulations of the posterior distributions of $\theta_{CFZ533} - \theta_{SoC}$ and compared to the thresholds for the levels of proof.

The prior distributions will be assumed to be a non-informative Beta(1/3,1/3) for θ_{CFZ533} and an informative prior of Beta(1, 13) for θ_{SoC} .

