Data for CFZ533 administration and concomitant therapies will be listed by treatment group and patient. The duration (days) of CFZ533 study medication administration will be summarized and listed. The duration will be calculated by subtracting the date of the last administration of study medication from the date of first administration and then adding the dosing interval for CFZ533. In calculating the duration of treatment, days of temporary interruption of study medication for any reason will be included, i.e, any days of interruptions will not be excluded from the duration of treatment. Further, the frequency of dose changes (including temporary dose interruption) will be presented by reason for the change.

Average daily doses of each treatment will be presented in a summary table and will be listed by treatment and patient. “Zero” will be used for periods of temporary interruption of study medication for any reason.

The number and percentage of patients who prematurely discontinued study medication will be summarized by reason for discontinuation.

If the number of events allow, Kaplan-Meier (KM) estimates of time to discontinuation of study medication curve will be constructed and presented graphically. In this analysis, patients

who have not discontinued study medication will be censored with the censoring time as defined by the last contact day.

Concomitant immunosuppressants

The dose of administered Basiliximab, MMF, Tac and CS will be listed by treatment and patient.

The dose of antibodies used for the treatment of acute rejection episodes will be summarized by treatment and listed by treatment and patient.

Other co-medications

Concomitant medications, other than immunosuppressants and CS mentioned above, will be listed by patient and summarized by therapeutic class and preferred term by presenting the number and percentage of patients using each medication for each treatment group.

Calculated eGFR

The main safety endpoint is calculated eGFR.

Patients will be considered as “on treatment”, whilst they are taking their assigned randomized treatment. If a patient switches to an alternative treatment or stops taking their assigned randomized treatment, this data will be excluded from the summaries, figures and analysis for eGFR data.

Calculated eGFR as determined by the central lab will be summarized by visit. The calculated eGFR will be presented graphically to show the overlaid patient profiles and mean profile over time.

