The following imputation method will be applied at each relevant timepoint for patients with missing eGFR values:

1. Patients that lose their graft before the timepoint in question will be assigned a value of zero for their missing eGFR value.
2. Patients that die or are lost to follow-up with a functioning graft before the timepoint in question will have an imputed value using the last-observation-carried-forward (LOCF) method.

Graft loss patients do not have a functioning graft, hence the lowest possible eGFR value (zero) will be assigned to such patients with missing eGFR values. In contrast, patients that die with a functioning graft, die for different reasons such as suicide, car accidents, cancer, therefore if they have a missing eGFR value, an imputed value using the LOCF method will be used. Similarly, patients who are lost to follow-up and have renal function, but are missing a Month 6 or Month 12 value for various reasons (e.g. moving from the area or not being able to make the site visit during the Month 6 or Month 12 visit) will have an imputed value using LOCF method for any missing eGFR value.

The mean eGFR results will be estimated from a longitudinal repeated measures mixed effects model using all the individual data collected until the timepoint of interest (1st IA Month 3 visit, 2nd IA Month 6 visit) whilst the patient is on treatment. From the model, estimates of the average at the timepoint of interest, treatment difference and 90% confidence

intervals will be obtained. The model will include fixed effects for treatment, time, donor age, donor type (living or deceased) and donor characteristic, treatment by time interaction and donor type by treatment by time interaction. An unstructured variance-covariance structure shall be used, however in the case that the model fails to converge, alternative structures would be tested. The estimates of the adjusted means and two-sided 90% CIs obtained from the model will be plotted over time.

The donor characteristic is a category that could have the result of “standard” or “expanded”.

Vital signs

All vital signs data will be listed by treatment, patient, and visit/time and if ranges are available abnormalities (and relevant orthostatic changes) will be flagged. Summary statistics will be provided by treatment and visit/time.

ECG evaluations

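### eGFR is compared on treatment only, with no visible all-data comparison beside it, and the SAP does not settle whether graft-loss zeros enter its only modelled comparison

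*SAP*

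**What the plan says.** **Protocol.** Section 9.5.3 sets a default: "Unless otherwise specified, safety analyses include all data collected, including after discontinuation of randomized treatment". Section 9.5.3.1 then specifies eGFR, the key secondary and safety variable, on the Full Analysis Set: "This will be evaluated at Month 12 by comparing the mean eGFR values between groups". Two of its handling rules matter here: "Patients that lose their graft will be assigned a value of zero for their missing GFR value", and "For patients that discontinue randomized treatment the eGFR will be considered missing after applying the windows". Those windows sit in section 9.4.1 and are blacked out. Death or loss to follow-up with a functioning graft is handled by LOCF. Section 9.7 bases evidence of renal benefit on an 80% interval and takes 6.5 mL/min/1.73 m² as the smallest relevant benefit.

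**SAP 7.1.2, Calculated eGFR.** "If a patient switches to an alternative treatment or stops taking their assigned randomized treatment, this data will be excluded from the summaries"; the same sentence covers figures and analysis. Imputation follows, at each relevant timepoint: "Patients that lose their graft before the timepoint in question will be assigned a value of zero for their missing eGFR value". LOCF is kept for death or loss to follow-up with a functioning graft. The next paragraph gives the only visible eGFR model, a repeated-measures mixed model with 90% intervals. It uses data collected up to the timepoint of interest ("1st IA Month 3 visit, 2nd IA Month 6 visit) whilst the patient is on treatment").

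**Exits and follow-up.** Protocol 5.5.5 links stopping study treatment to certain severe or steroid-resistant rejections, to biopsy-proven BK nephropathy and to permanent dialysis. Protocol 5.5.10 and section 6 keep such patients in the study to Month 12 in Part 2, where possible. SAP 6.1.4 records: "During data review, it was noticed that some patients were switched from the randomized treatment to another regimen".

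**The concern.** Two things are at stake.

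First, some patients leave treatment because of what is happening to the graft. Their earlier values stay in, but their later ones do not. The on-treatment difference can then depart from the difference between patients started on each regimen, and no visible output gives the second quantity. For tBPAR, the SAP reacts to switching with more weight on Kaplan-Meier and a supportive Poisson model. For eGFR, no supportive analysis is visible.

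Second, the protocol's mean comparison scores a failed graft as zero. The SAP repeats the rule and then describes a model whose data definition seems to shut those zeros out. A renal-benefit statement could then rest on functioning grafts without saying so.

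**Working it through.** **1. Do the zeros reach the model?**
- Imputation rule (SAP 7.1.2): zero for missing eGFR after graft loss, at each relevant timepoint.
- Model input (next paragraph): data collected while on treatment. An imputed zero is not a collected value.
- Protocol 5.5.5: permanent dialysis or retransplantation ends study treatment, so visits after graft loss normally fall off treatment. The exception is a visit after the loss but before the formal stop.

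The rule says the zeros exist; the model's data definition, read literally, excludes them. No sentence says which outputs use them. A switcher with a working graft who stays in follow-up meets neither imputation rule and has no later value in the model.

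**2. The plan's own precision figures.** Protocol Table 9-2 gives half-widths of 4.0/4.5/5.0 (80%) and 6.2/7.0/7.7 (95%) for SD 16/18/20. The formula is half-width = t × SD × √(1/n₁ + 1/n₂).
- With n = 53 per group: 4.01/4.51/5.01 and 6.16/6.93/7.70. Of the 30 printed intervals, 25 match; the five for SD 18 at 95% differ by 0.1 per limit.
- With n = 52.5 per group (75 × 0.7, an inference), all match. Normal quantiles do not fit every cell.

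**3. Same formula at Part 2 size (30 v 15).** √(1/30 + 1/15) = 0.316, with 43 degrees of freedom.

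| SD | 80% (protocol) | 90% (SAP) |
|---|---|---|
| 16 | 6.6 | 8.5 |
| 18 | 7.4 | 9.6 |
| 20 | 8.2 | 10.6 |

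If only 21 and 11 patients contributed (about 30% off treatment), the ranges would be 7.8 to 9.8 and 10.1 to 12.6.

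**4. One graft loss left out instead of scored zero.** The arm mean shifts by m/n, where m is mean eGFR among functioning grafts. The documents give no mean; I assume 50 to 60.
- Arm 2A: 50/30 = 1.7 to 60/30 = 2.0.
- Arm 2B: 50/15 = 3.3 to 60/15 = 4.0.

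The mixed model keeps earlier on-treatment values, which softens this. If the last on-treatment value were 20 and the visit correlation 0.7 (both assumed), the implied later value is m + 0.7(20 − m) = 29 to 32. The shift is then 1.0 to 1.1 (n = 30) or 1.9 to 2.1 (n = 15).

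**5. Direction.** Assume a control mean of 55 and a difference of 6.5 among functioning grafts.
- One loss in Arm 2A scored zero: 61.5 × 29/30 − 55 = 4.45.
- One loss in control scored zero: 61.5 − 55 × 14/15 = 10.17.

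**6. Exits without graft loss.** On-treatment minus all-data difference = pA·dA − pB·dB, where p is the proportion leaving each arm and d is how much lower leavers' later eGFR is (assumed 10 to 20).
- 30% leave both arms (borrowed from Table 9-2, not a Part 2 switching rate): 0.3 × 10 − 0.3 × 20 = −3.0, up to +3.0. It is 0 if the falls are equal.
- Unequal exits (assumed 6 to 9 of 30 v 0 to 2 of 15): (6/30) × 10 − (2/15) × 20 = −0.7, up to (9/30) × 20 = +6.0.
- If half the fall is seen before the switch and the correlation is 0.7, multiply by 1 − 0.7 × 0.5 = 0.65: about −2.0 to +2.0, and −0.4 to +3.9.

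**The case against.** **The on-treatment restriction is a choice, not an error.** This stands. A reader might infer that the SAP departs from the protocol or breaks the all-data default for safety analyses. It does neither: the default yields where something else is specified, and protocol 9.5.3.1 itself sets eGFR to missing after discontinuation. Values after conversion to standard of care partly measure standard of care, so the on-treatment model has a clear use. What remains is the lack of a second analysis beside it.

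**The zeros may be meant to enter.** The imputation rule stands directly before the model. Off-treatment values could be removed, become missing, and then be imputed as zero after graft loss. That reading is coherent, so it would go too far to say that the SAP drops the zeros. The text is in conflict and needs a ruling.

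**Failed grafts are reported elsewhere.** True. Composite failure is a secondary variable (SAP 6.2.1), graft loss and graft loss or death are analysed in SAP 6.2.3, and the first DOOR ranking in SAP 7.1.2 places graft loss explicitly. A reader might infer that graft loss is hidden; it is not. None of these is an eGFR difference, however. The general laboratory summaries and the creatinine-based DOOR ranking are not one either.

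**Text is redacted.** The on-treatment window, the Part 2 assessment schedule and parts of the SAP are blacked out. The claim is therefore limited to what is visible.

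**The sizes are assumed and smaller than the noise.** Also true: every shift in steps 4 and 6 is below 6.5 and below the corresponding half-widths at 30 v 15.

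**Conclusion.** The point holds as a cheap improvement. No between-arm comparison of all collected eGFR is visible, and SAP 7.1.2 contradicts itself on whether graft-loss zeros reach its only visible modelled comparison. Read literally, the estimate behind a renal-benefit claim can leave out failed grafts that protocol 9.5.3.1 counts as zero.

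One such loss is worth 1.7 to 2.0 in Arm 2A or 3.3 to 4.0 in control under an assumed mean of 50 to 60, or roughly half that if a low last value stays in the model. The t-based half-widths are 6.6 to 8.2 (80%) and 8.5 to 10.6 (90%). A single loss would not decide the result alone, but it is not negligible against a 6.5 benchmark.

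A reader might infer that the on-treatment rule favours CFZ533. The documents do not support that: the sign depends on which arm has the losses and switches, and the number of switches is not given.

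**What to change.** In SAP 7.1.2:

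1. Keep the on-treatment model.
2. Add a between-arm analysis of all collected eGFR regardless of switch, with zero at every visit after graft loss and each switcher kept in the arm of the initial treatment.
3. State which outputs use the zeros and the LOCF values, and make sure that at least one between-arm comparison includes the zeros.
4. Report both analyses before any conclusion on renal benefit.

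The cost is wording and one added analysis, with no new visits. The zeros need only the graft-loss date, which the Graft Loss eCRF already captures. There are two drawbacks. Post-switch values dilute the CNI-free effect, which is why the on-treatment model stays. Off-treatment creatinine may also be sparse: follow-up is where possible, and the Part 2 schedule cannot be read.

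Separately, reconcile the laboratory source. Protocol 9.5.3.1 uses local creatinine for all renal function analysis, while SAP 7.1.2 takes eGFR from the central laboratory. The SAP cites protocol v02, so this may be a version difference. Before naming one source, check that it has a Study Completion sample. The Part 2 blood log in Appendix 1 shows no local volume at Day 364 and 2.5 mL central of unstated purpose. The printed totals agree with that (20 × 19 = 380; 20 × 6 + 2.5 = 122.5).

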1.3.2 Secondary objectives

- To assess the safety and tolerability of CFZ533 administered chronically in combination with MMF and CS up to 3 months against a control
- To assess the PK of multiple IV doses of CFZ533 during the 12-month treatment period
- To quantify the magnitude and duration of peripheral blood CD40 occupancy (free CD40 and total CD40 on B cells) during the treatment period following multiple IV doses of CFZ533
- To compare renal function in CFZ533 treatment arms to control at Month 3 post-transplantation as assessed by:
 - Estimated GFR
 - Proportion of patients with eGFR < 60 mL/min/1.73 m²
 - Proportion of patients with negative eGFR slope
- To evaluate the immunogenicity of multiple IV doses of CFZ533 via the quantitative analysis of anti-CFZ533 antibodies
- To quantify the change from baseline and recovery of peripheral blood total soluble CD40 during the treatment period following multiple IV doses of CFZ533.

[figure not shown]
The assessment of safety and tolerability and comparison of renal function will also be assessed at Month 12.

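### Missing eGFR after death or loss to follow-up is filled by last observation carried forward, and at Month 12 no other handling is stated, although the SAP plans a mixed model that does not need it

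*SAP*

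**What the plan says.** **Imputation.** Under calculated eGFR, SAP 7.1.2 sets two rules for missing values at each relevant timepoint. For graft loss: "Patients that lose their graft before the timepoint in question will be assigned a value of zero". For death or loss to follow-up: "Patients that die or are lost to follow-up with a functioning graft before the timepoint in question will have an imputed value", which is the last observation carried forward. Protocol 9.5.3.1 agrees: "Patients that die or are lost to follow-up with a functioning graft will have an imputed value using the last-observation-carried-forward (LOCF) method". The SAP describes the second group as patients "missing a Month 6 or Month 12 value for various reasons", and both documents give inability to attend the visit as an example.

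**Model.** The same SAP section then has mean eGFR "estimated from a longitudinal repeated measures mixed effects model using all the individual data collected until the timepoint of interest". The timepoints and restriction given are "1st IA Month 3 visit, 2nd IA Month 6 visit) whilst the patient is on treatment". The covariance is unstructured. The section does not say whether LOCF values or graft-loss zeros enter the model or serve only the by-visit summaries.

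**Timepoint.** Protocol 9.5.3.1 calls eGFR the key secondary and safety variable and compares group means at Month 12. SAP 1.3.2 adds: "The assessment of safety and tolerability and comparison of renal function will also be assessed at Month 12". Month 12 is not among the timepoints named for the model.

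**Related rules.** Both documents drop eGFR data after a patient leaves randomized treatment. Protocol 5.5.12 says a subject is not to be considered lost to follow-up until the scheduled end-of-study visit would have occurred.

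**The concern.** LOCF is reasonable only if the outcome is flat after the last observed value. The protocol itself shows that renal function is not flat early after transplantation. Appendix 7 applies its creatinine limits only after Week 4, Section 5.5.5 defines delayed graft function by dialysis within seven days, and Section 1.1 speaks of delaying tacrolimus until renal function has recovered. A value last seen in that phase is not a Month 6 or Month 12 value.

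The rule also treats a guess as a measurement. If carried values entered the model, they would pull the means towards early levels and make the intervals too narrow. If they stay out, the model already does what is needed at Months 3 and 6, but nothing equivalent is written for Month 12. Two programmers could follow this text and report different Month 12 differences for the key secondary variable.

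**Working it through.** **1. The plan's own eGFR figures.** The documents give no figure for the effect of LOCF. The only precision figures are in protocol Table 9-2 (53 per group). The formula is d ± t(104 df) × SD × √(2/53). For SD 16 and d = 4.0 it gives −0.01 to 8.01 (80%) and −2.16 to 10.16 (95%); the table has −0.0 to 8.0 and −2.2 to 10.2. Checked at d = 4 and 7 for each SD, the 80% limits match to one decimal and the 95% limits agree within 0.1. The SD range of 16 to 20 is used below.

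**2. Inputs.** Arms of 30 and 15 (SAP 1.4.2). Lower limit of relevant benefit 6.5 mL/min/1.73m2 (protocol 9.7). Part 2 laboratory draws every 28 days from Day 57 to Day 337 (protocol Appendix 1). The documents give no eGFR trajectory and no rate of death or loss with a functioning graft, so gaps and rates below are assumptions.

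**3. Age of the carried value.** A patient who misses only Month 6 or Month 12 carries a value about 28 days old. Only a patient who leaves in the first weeks carries one from the recovery phase.

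**4. One early exit.** Shift in the arm mean = gap / n, for a gap of 10 to 30.

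| Arm | n | Shift | Share of 6.5 |
|---|---|---|---|
| Control | 15 | 10/15 = 0.7 to 30/15 = 2.0 | 10% to 31% |
| CFZ533 | 30 | 10/30 = 0.3 to 30/30 = 1.0 | 5% to 15% |

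**5. Effect on the difference.** Shift = −(pA·gA − pB·gB). Here p is the share of an arm imputed and g is the value at the timepoint minus the carried value. A is CFZ533 and B is control. With the same g of 5 to 20 in both arms:

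| Imputed, CFZ533 v control | Shift |
|---|---|
| 3/30 v 1/15 | −0.2 to −0.7 |
| 10% v 0% | −0.5 to −2.0 |
| 30% v 30% | 0 |
| 30% v 10% | −1.0 to −4.0 |

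If the carried value lies above the later one, g is negative and the sign reverses.

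**6. Scale.** At 30 v 15 the standard error is SD × √(1/30 + 1/15), or 5.06 to 6.32 for SD 16 to 20. With t(43 df) the 90% half-width, the level the SAP uses, is 8.5 to 10.6.

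**7. Simulation.** 600 runs per scenario, 30 v 15, SD 18, true difference 6.5. The assumed control mean rises 35, 45, 48, 49, 50, and the treatment effect builds up over the same visits. Dropout is unrelated to eGFR, and the last value comes from one of the first three visits.

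| Imputed, CFZ533 v control | LOCF | Mixed model, observed values |
|---|---|---|
| 10% v 7% | 6.2 | 6.7 |
| 20% v 7% | 5.5 | 7.1 |
| 30% v 30% | 5.6 | 6.2 |
| 30% v 10% | 4.0 | 6.7 |

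The Monte Carlo standard error is about 0.25, so the first row does not separate the methods. In the second row both estimates run high. The average gaps under these assumptions are 10.58 (CFZ533) and 7.33 (control), so the formula gives 6.5 − (0.20 × 10.58 − 0.07 × 7.33) = 4.9 for LOCF. Equal dropout at 30% still shifts LOCF, because the gaps differ between arms.

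**The case against.** **The model most naturally excludes LOCF values.** A carried value is not collected, and nobody is on treatment after death. A reader might infer that imputed values do enter the model and bias its Month 3 and Month 6 estimates. The text does not support that; it only fails to rule it out. It is also no defect that raw by-visit means and adjusted model means differ. This objection stands for Months 3 and 6. It does not reach Month 12. The two timepoints may be listed only because they are the interim analyses, but then the final one still has to be named.

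**The rule reaches few patients.** Treatment switchers are excluded rather than carried forward, off-treatment patients stay in the study, and under protocol 5.5.12 almost nobody is formally lost before the end. This stands as a limit on size. It also leaves unclear what triggers LOCF for loss to follow-up at the Month 3 and Month 6 analyses.

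**The size rests on assumptions.** This stands. A reader might also shrink the control arm by Table 9-2's 30% dropout (15 × 0.7 = 10.5) and obtain up to 30/10.5 = 2.9 per patient. That dropout belongs to a table built on 53 per group, not to this design. Nor do the documents support uneven exits as large as 30% v 10%.

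**A mixed model is no complete answer.** It assumes missing at random, implicitly estimates eGFR past death, and leaves the graft-loss zeros unsettled. All of this is true, and the remedy has to cover it.

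**Conclusion.** The concern holds in limited form. LOCF is a poor main rule for an outcome that recovers over the first weeks, and it is the only handling stated for death or loss with a functioning graft at Month 12. The better method is already in the SAP.

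One early exit can move an arm mean by 0.3 to 2.0 mL/min/1.73m2, assuming a gap of 10 to 30. The effect on the difference is about 0.2 to 0.7 with few, roughly balanced exits (assuming a gap of 5 to 20), well inside a 90% half-width of 8.5 to 10.6. It reaches 1 to 4 only if exits are markedly uneven.

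Two stronger readings should be set aside. A reader might infer that every missed visit imports an early value, but a single missed visit carries one about a month old. A reader might also infer that the direction depends only on the patient's arm, but it depends as well on whether the carried value lies below or above the later one. The tBPAR primary analysis is unaffected.

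**What to change.** In SAP 7.1.2 and protocol 9.5.3.1:

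- Name the mixed model on observed on-treatment values, under missing at random, as the main eGFR analysis at Months 3, 6 and 12, and state that no LOCF value enters it.
- State that for deaths the model estimates eGFR as if the patient had lived, or define another estimand.
- State whether graft-loss zeros enter the model or appear only in a separate summary.
- Keep LOCF only as a labelled sensitivity analysis. Say which value is carried and, given protocol 5.5.12, what counts as loss to follow-up at Months 3 and 6.

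The cost is wording in two documents. The model is already planned, needs no new data, and has only to be run at Month 12 as well. The downside is reliance on missing at random, which these data cannot confirm.
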